Published studies in MS, including the work in our lab at Stony Brook Medicine, show tDCS to be a tolerable and safe treatment approach. Members of the core physician group and team at the MS Center are Neurology specialists with extensive experience in the assessment of neurology patients, including capacity to consent for numerous clinical drug trials where there is a substantially greater potential risk posed than what are the known risks for tDCS. Therefore, taken together, we do not believe that the use of tDCS represents a situation where an independent party would be needed.

Process to Document Consent in Writing

After review of the consent form and prior to the start of the first session, the PI or one of the trained study staff members will obtain written consent with a signature of the patient on the consent form. All original signed consent forms will be maintained in the study file, separate from the participant data.

Subject Capacity

All participants will be confirmed to have the capacity to provide consent by a member of the core physician group as described above. Further, those participants with estimated premorbid intellectual functioning and/or impaired reading ability (as determined by the WRAT-4 Reading Subtest), and those with severely impaired information processing speed (as determined by the SDMT) will be excluded.

Debriefing Procedures

No information will be purposely withheld from the subjects. A clinical neuropsychologist (PI) and the treatment team will be available to answer any questions concerning the tests and results, and provide initial feedback as warranted, including referral for clinical neuropsychological assessment.

Consent Forms

Participants will receive a NYU consent form to review and sign prior to participating in the study.

Documentation of Consent

The PI is responsible for ensuring that valid consent is obtained and documented for all subjects. An enrollment log will be maintained and consent forms will be kept in secure location separate from the participant's data.

Costs to the Subject

If subjects choose to participate, the cognitive remediation sessions will be provided to them without cost for that care. The MS Center medical secretary who oversees billing authorization for clinical neuropsychological service will perform insurance authorizations. Following procedures for clinic appointments, prior authorization will be obtained and the participant will be informed of any potential costs prior to scheduling and enrollment. Both the cognitive remediation and tDCS will be covered by the research team, further no additional sessions will be required for research purposes. If subjects have been referred for other clinical services in addition to cognitive remediation or if the clinical review of their case indicates that other treatments would be appropriate, these treatments would be provided at a cost to subjects based upon their insurance coverage. Subjects will be informed of their payment responsibilities before they are enrolled in the study during the pre-screening phone conversation (see Section IX, Process of Consent).

Payments to the Subject

Subjects will not be compensated for their participation in the study.

Risk to Participants

As described above, tDCS poses low risks to participants and our protocol is well-tolerated [18]. To our knowledge, hundreds of tDCS studies in the US have all been designated Non-Significant-Risk (NSR) the lowest risk level (devices that are not: intended as an implant with potential for serious risk to health, safety, or welfare of subject; purported or represented to be for use in supporting or sustaining human life with a potential for serious risks; for use of substantial importance in diagnosing, curing, mitigating, treating disease or otherwise preventing impairment of human health with potential for significant risk; otherwise presents significant risk to the health, safety, or welfare of a subject). For these reasons, the Soterix Mini CT, as used in this study, also qualifies as a NSR device. While tDCS remains an investigational technique (simply because no company has applied to the FDA for approval to market tDCS for any given indication), tDCS is a broadly reproduced and tested techniques that is considered effective in modulating brain excitability in a manner that may support learning and with adverse events (different than sham) limited to tingling, itching, and redness that dispel after stimulation stops. In a prior study of use in a vulnerable population (developmentally disabled children), the FDA issued a NSR for tDCS device (see attached letter). The letter provided as an example of the FDA's designation of tDCS devices as having abbreviated-IDE. Because of its prior designation of tDCS devices as abbreviated-IDE, trials do not typically seek further declaration. In the letter provided, [name] specifically sought FDA review of the trial due to the use of tDCS in a vulnerable population (developmentally disabled children). To date, hundreds of trials have been designated as non-significant-risk by IRB review which provides its abbreviated IDE status. Results of completed trials, including our own work in MS using this protocol, have supported the risk designation provided by IRBs. The Stony Brook Medicine IRB confirmed the NSR and abbreviated IDE status of tDCS for our study.

and others at the institution. We have learned that the NYU IRB has also confirmed tDCS devices (including those manufactured by Soterix) as having an abbreviated-IDE for current ongoing studies at this institution for other indications.

The safety of this technique has been addressed and tested by multiple researchers (Fregni, et. al. [59]; Nitsche, et al. [60]; Priori, et al. [15]) who have concluded that tDCS, as applied in a manner similar to our proposed protocol, induces only temporary mood, cognitive / motor effects, and no negative side effects.. For example, researchers at the National Institute of Neurological Disorders and Stroke (NINDS), Iyer et al. [17] conducted a safety study on tDCS, investigating 20-minute sessions of 1 mA and 2 mA current stimulation with healthy controls (n=103). No negative effects were identified. Nitsche and colleagues found no measurable structural changes in brain tissue due to tDCS [61]. In a meta-analysis of over 200 tDCS studies conducted from 1998 to 2010, 56% of studies mentioned adverse events, which were generally minor. The most commonly reported side effects included itching, tingling, headache, burning sensation and discomfort limited to the scalp site where the tDCS electrodes were applied. To date, there have been no reports of seizures induced by tDCS¹⁴. Importantly this is the case in normal volunteers, but also in different populations of patients, including patients with disorders where there might be an increased risk of seizures (e.g. Alzheimer's disease, recent stroke, epilepsy). A study from NYU on the use of tDCS in patients with epilepsy [62] encountered no increase in complications of tDCS in the patients as compared with controls. Specifically, there were no instances of seizures induced by tDCS.

Participants in all groups may find the questionnaires time consuming and potentially bothersome. Neuropsychological testing and the computer training sessions may, in some individuals, be stressful or anxiety producing. There is a small risk of loss of confidentiality. Participants will be assigned a study ID and their name will not be used on any of the information collected. The program used for brain training games will not collect any personally identifiable information. The results of these data collected may be used for publication but will not include the participants' names. Hardcopies of the data files will be kept in secure, locked files and data will be entered in a secure, NYU approved database.

Benefits to Participants

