Figure 1: Tolerability across >500 active RS-tDCS sessions

From our high rate of tolerability and great interest from patients and physicians in previous studies, we believe expanding our tDCS protocol to open-label trials for general neurological disease offers the potential for direct clinical benefit.

While we have focused the development of our methods in participants with MS and PD, both cognitive remediation along and in combination tDCS treat the symptom of cognitive impairment as it occurs across a wide range of disorders [23, 25, 43].

III. SPECIFIC AIM

Specific Aim: To test the feasibility and tolerability of augmenting cognitive remediation with tDCS. Once referred to receive cognitive remediation, eligible and interested participants (n=100) will receive up to sixty daily 20-minute sessions of active (up to 4.0 mA) tDCS paired with their completion of the cognitive tasks.

We will determine the dosing parameters for optimal treatment across individual participants, depending on the nature and severity of baseline deficits.

The primary outcome for feasibility will be the number of participants completing at least 80% of the targeted number of sessions. Secondary outcomes will be analysis of tolerability and participant-reported side effects.

IV. DESCRIPTION OF THE PROTOCOL

A baseline neurological and neuropsychological assessment will be completed in-clinic before patients begin the cognitive remediation program. Pending the results of these assessments, participants who are eligible for cognitive remediation will be referred to the study. For the 60 cognitive remediation sessions, eligible participants will receive 20 minutes of active tDCS stimulation (up to 4.0 mA, montage to be determined based on clinician input) while they complete the cognitive training tasks. Once the participant has completed his/her 60 sessions a follow-up neuropsychological assessment will be completed.

V. SUBJECT SELECTION

Characteristics of the Research Population

We will enroll a total of n=100 adults (ages 18 and over) with a clinician referral to receive cognitive remediation.

Eligibility Criteria

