***Note PI assessment for eligibility may occur either before or at the baseline visit**

Prior to tDCS training, the tests and evaluations detailed in Table 2 will be administered.

tDCS aptitude screen and tolerability test:

- **tDCS Aptitude:** Participants will first complete an aptitude test to confirm that they have the cognitive and motor skills required for headset placement.

With instruction of the study technician, participants will be asked to insert the sponges onto the headset and place the electrodes into the sponges. The technician will determine whether or not the participant is qualified to proceed. Participants will not be allowed to proceed if they are not able to correctly either 1) attach sponges to headset or 2) place electrodes into the sponges.

tDCS Tolerability: The study technician will next directly place the headset and then initiate a one-minute test session, with 30 seconds of ramp-up to target, following by 30-second ramp down. The tolerability test will first take place using 2.5 mA stimulation. If the participant tolerates and agrees, 3.0 will be tested; again

if the participant tolerates and agrees, the next increment of 3.5 mA will be tested; as follows, increases will be made to 3.5 and 4.0 mA respectively (note: the option for increase is device-dependent; some current devices have a maximum of 2.5 mA programming). Alternatively, if the participant cannot tolerate 2.5 mA, stimulation will be based on highest amplitude tolerated, following 0.5 mA decrements (with 2.0, 1.5., and 1.0 mA stimulation offered). Once the tolerable dose is established, it will remain constant throughout the study. If the participant cannot tolerate any offered stimulation levels, they are excluded from the study.

- A total of 20 x 20 minute sessions is targeted, with the option for up to 60 x 20 minute sessions to be completed. The minimal goal of 20 sessions completed will continue up to 60 treatment sessions if jointly agreed between the study participant and referring clinician.

Remotely Monitored Study Sessions:

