Outcome Measures: Before and after each session, participants will complete brief measures to monitor for any stimulation-related events. Brief measures will also be given to monitor any therapeutic or behavioral effect of the tDCS stimulation. To further inform tolerability of stimulation sessions, a pain scale will be administered before, during, and after each session. Participants will also complete baseline and study-end inventories of cognitive and behavioral

measures to help guide power estimates for the future trials. A summary of outcome measures can be found in Table 2.

All remotely-supervised sessions will be completed while connected to a video session with the study technician. The protocol is designed to have a decision-tree series of checkpoints that must be met in order to proceed at each step (Figure 2). These checkpoints address compliance (attendance, ability to complete the procedures as instructed, following the study guidelines) and tolerability (at any time, if any predefined events are reported, or if pain crosses a threshold the participant will be discontinued).

Table 2. Study Outcome Measures

Test	Screening	Baseline	Daily Study Sessions	Study End/Follow-up Visit	Post Study Survey (at least 1 month after study end)
Medical Clearance	x	x			
Wide Range Achievement Test (WRAT-4)	x				
Symbol Digit Modalities Test (SDMT)	x	x		x	
tDCS Aptitude Test		x			
tDCS Tolerance Test (4.0, 3.5, 3.0, 2.5, 2.0, or , 1.5, or 1.0 mA)		x			
PROMIS Measure of Fatigue, Mood and Health-Related Quality of Life		x		x	x
Cogstate		x*		x*	
Test of Everyday Cognitive Ability		x*		x*	
King Devick		x*		x*	
Hand grip and pinch strengths		x*		x*	
Symptom Specific Measures (Cognitive and behavioral)		x	x	x	
Cognitive Linguistic		x*		x*	

Cognitive remediation augmented with tDCS
Study # s16-01810

Quick Test, The Communicative effectiveness Index, Western Aphasia Battery Part 2					
Positive and Negative Affect Scale (PANAS)		x	x	x	x
Visual analog scale for pain (pre-, mid- and post-session)		x	x		
Tolerability questionnaire administered by study staff (pre- and post-session)		x	x		
Safety and tolerability questionnaire - self-report (pre- and post-session)		x	x		
Score for Computerized cognitive games (daily)			x		
Participant evaluation of study procedures and report of their experience				x	x
Count of successful tDCS sessions (confirmation code by session days)				x	

*- Optional measure

VII. STUDY LOCATION

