We will utilize operating procedures for reviewing patient safety data and source data generated from this study. This will include weekly meetings between the PI, the Co-I ([name]), and study coordinators. At these meetings, the entire research team will review the clinical ratings, assessments, clinical course, and medical records for each subject. Consideration of dropping any patient from the study for any reason will be discussed. If after the completion of the first 20 subjects the compliance is significantly low, the study will be put on hold and reviewed. Based on the extensive body of literature using tDCS across a range of conditions, and our initial participants studied to date (completed at Stony Brook Medicine), we have had >94% compliance in the active condition. Due to our success with compliance in previous studies, we do not expect severe compliance issues. Still, we are prepared to deal with compliance problems, if there is significantly poor compliance, we will be able to identify reasons including tolerability as well as symptom experiences. Tolerability is measured before, during and after each session and all participants will be monitored for all sessions. Safety is carefully addressed in our protocol with a series of stop criteria and clearly defined action items.

Specific attention will be given to data quality and timeliness, HIPAA-complaint, safe storage of data, and data backup of electronic source data. Attention will also be given to participant recruitment, accrual and retention, participant risk versus benefit, adverse events, and other factors that can affect study outcome, including scientific or therapeutic developments that may have an impact on the safety of the participants or the ethics of the study.

Definition of Adverse Events (AE)

An **adverse event** (AE) is any symptom, sign, illness or experience that develops or worsens in severity during the course of the study. Inter current illnesses or injuries should be regarded as adverse events. Abnormal results of diagnostic procedures are considered to be adverse events if the abnormality:

- results in study withdrawal
- is associated with a serious adverse event
- is associated with clinical signs or symptoms
- leads to additional treatment or to further diagnostic tests
- is considered by the investigator to be of clinical significance

Definition of Serious Adverse Events (SAE)

Serious Adverse Event

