Adverse events are classified as serious or non-serious. A **serious adverse event** is any AE that is:

- fatal
- life-threatening
- requires or prolongs hospital stay
- results in persistent or significant disability or incapacity
- a congenital anomaly or birth defect
- an important medical event

We will submit study data safety monitoring reports to the IRB after 10 participants are enrolled, and follow with reports for each further increment of 10 active enrollees.

Statistical Analyses

Analyses will be completed with IBM SPSS v. 23. Means, medians, standard deviations (SD) will be compared between subgroups on the measures using conventional cut-off points for each of the symptoms will be compared. Our sample size (n=100) was determined by a power analysis indicating over 90% in determination of feasibility and tolerability.

Specific Aim 1 will be tested by assessing the compliance (<80% sessions completed) of study participants within groups established by disease, age, EDSS scores etc. We will also assess any reported side effects of active tDCS treatment to determine general tolerability

Secondary outcomes will be used to compare the groups in change in performance on the additional measures listed in Table 2. In addition, performance on the WM CT will be analyzed across training sessions, including time to advance to a new level and overall levels achieved. Similar analysis as what have been planned for the primary outcome will be performed for comparing the change in these secondary outcomes between before and after the completed sessions.

Neurological clinical features (age, gender, disease, treatment, disease duration) will be compared by correlational analysis.

IX. SUBJECT RECRUITMENT AND CONSENT/ASSENT

Subject Identification, Recruitment and Consent/Accent

Method of Subject Identification and Recruitment

NYU Langone Medical Center has an extensive recruitment base. Patients who are seen by medical staff at NYU Langone Medical Center, who fit the eligibility criteria, will be referred for the study by the study PI, Co-I, and sub-investigators. If the patient is interested and agrees, then a member of the study staff will contact them. Once a patient is identified, study staff will meet with the patient or call them to provide additional information regarding study participation. After the patient has reviewed the consent form and asked all questions, and provides consent to participate, the patient will be enrolled in the study.

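### The over-90% power behind n=100 is undefined for tolerability and uncheckable for feasibility, and the Aim 1 analysis and session denominator do not match the primary outcome

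*Combined protocol and SAP*

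**What the plan says.** The sample size rests on one sentence in Section VIII, Statistical Analyses: "Our sample size (n=100) was determined by a power analysis indicating over 90% in determination of feasibility and tolerability". No significance level, sidedness, null proportion, expected proportion, test or dropout allowance for that calculation appears there or elsewhere.

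**Primary outcome.** Section III: "The primary outcome for feasibility will be the number of participants completing at least 80% of the targeted number of sessions". The same section makes tolerability and reported side effects secondary.

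**Written analysis.** Section VIII says Aim 1 will be tested by "assessing the compliance (<80% sessions completed) of study participants within groups established by disease, age, EDSS scores etc". On tolerability it adds: "We will also assess any reported side effects of active tDCS treatment to determine general tolerability".

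**Other criteria.** Section VI, Outcome Measures, has a rule for the individual: "if any predefined events are reported, or if pain crosses a threshold the participant will be discontinued". Section VIII, Data and Safety Monitoring Plan, has a study-level check: "If after the completion of the first 20 subjects the compliance is significantly low, the study will be put on hold and reviewed". No number is attached to it. That plan also reports earlier compliance above 94%, and Section II reports 95% completion.

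**Session target.** Section VI, under the Baseline Visit: "A total of 20 x 20 minute sessions is targeted, with the option for up to 60 x 20 minute sessions". Section IV: "Once the participant has completed his/her 60 sessions a follow-up neuropsychological assessment will be completed". Sections I, III and VI (Study Design) speak of up to 60 sessions.

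**The concern.** A power figure needs a hypothesis, and the hypothesis needs a defined endpoint. Here a single figure covers two outcomes. For tolerability there is no cohort hypothesis at all. For feasibility, the 80% in the primary outcome is the share of sessions that one participant must complete. It is not the share of participants that would make the programme feasible, and no such share is stated.

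Two further gaps bear on the same figure. The analysis written for Aim 1 is by subgroup, with no overall estimate or interval, although the outcome is a count over all participants. The denominator of that outcome is also not fixed, so two analysts could classify the same participant differently. At stake are the justification for n=100 and the reproducibility of the primary result.

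**Working it through.** **1. Can the stated figure be reproduced?** No. Of the quantities needed, only n=100 is given. One near match can be built with the one-sample normal approximation, n = [(z_α√(p0(1−p0)) + z_β√(p1(1−p1))) / (p1−p0)]². With p0=0.85, p1=0.94, one-sided α=0.05 and 90% power:

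(1.645×0.3571 + 1.282×0.2375) / 0.09 = 9.91, and 9.91² ≈ 98.2, so n=99, with 90.6% power at n=100.

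No 85% cohort bar appears in the documents, so the match may be coincidence.

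**2. How far does the feasibility power depend on the missing inputs?** All inputs except n are assumptions. The true rate of 94% is borrowed from the earlier compliance figure in Section VIII, which is not defined as the share of participants reaching 80% of sessions. The 95% rate is borrowed in the same way from Section II. The method is an exact one-sided binomial test of H0: p ≤ bar. The critical value c is the smallest k with P(X ≥ k | bar) ≤ α, and power is P(X ≥ c | true rate).

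| Assumed bar | c at 2.5% / 5% | Power, true rate 94% | Power, true rate 95% |
|---|---|---|---|
| 80% | 89 / 87 | 98.3% / 99.7% | 99.6% / over 99.9% |
| 85% | 93 / 92 | 74.8% / 85.4% | 87.2% / 93.7% |
| 90% | 96 / 96 | 27.7% / 27.7% | 43.6% / 43.6% |

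The unstated bar alone moves power from about 28% to over 99%. Against an 80% bar, a true rate of 90% instead of 94% lowers power to 70.3% / 87.6%.

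**3. Tolerability.** The stop rule in Section VI acts on one participant at a time, and Section VIII only says that side effects will be assessed. With no cohort null, alternative or test, there is nothing to calculate. The stop-criteria figure was not legible in the text reviewed, but the surrounding text applies it to individuals.

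**4. Outcome against analysis.** Section III counts participants at or above 80% of targeted sessions and mentions no groups. Section VIII describes testing within groups, leaves the list of groups open, and writes the cut-off as below 80%. No overall proportion with an interval is written.

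**5. Denominator.** 0.80 × 20 = 16 sessions; 0.80 × 60 = 48 sessions. A participant who stops at 20 is at 20/20 = 100% or 20/60 = 33%. One who agrees to continue towards 60 and stops at 40 passes the first cut-off (40 ≥ 16) and fails the second (40 < 48).

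**6. What n=100 does deliver.** Exact (Clopper-Pearson) two-sided 95% intervals: 80/100 gives 70.8–87.3%; 94/100 gives 87.4–97.8%. For 0/100 the upper limit is 1 − 0.025^(1/100) = 3.6%.

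**The case against.** The strongest reply is that this is a single-arm, open-label feasibility study, which needs no formal power, and that nothing shows the figure to be wrong. Both points stand. A reader might infer that the claim of over 90% is false, but the table does not support that: it holds comfortably against an 80% bar at a true rate of 94%. The difficulty is that the plan asserts power and gives no means of checking it.

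Other readings also go further than the text:

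- **That tolerability could not have been sized at all.** A study can be sized on the chance of seeing at least one event. With n=100 that chance is 90% for a true rate of about 2.3%, from 1 − 0.1^(1/100). The plan does not say it meant this, so the power is undefined as written, not undefinable.
- **That Aim 1 will be examined only within subgroups, or that subgroup power is claimed.** The plan says neither. The groups may be a breakdown of the overall count, but no overall estimate with an interval is written.
- **That 20 and 60 are equally supported as the denominator.** They are not. Section VI attaches the idea of a target to 20, and three sections describe 60 as a maximum. Section IV still conflicts, and no section says whether the target moves when a participant extends.
- **That the below-80% wording reverses the endpoint.** It may simply be the complement, non-compliance. It needs aligning and carries little weight.

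**Conclusion.** The point holds in a limited form. Power for tolerability is undefined as written, and this does not depend on any assumed input. Power for feasibility cannot be verified: at n=100 and an assumed 94% true rate it runs from 28% to 99.7% as the assumed bar moves from 90% to 80%. Those figures rest on an exact one-sided test and on treating an earlier compliance figure as the participant-level success rate, neither of which the plan states.

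The written Aim 1 analysis does not deliver an interval for the overall primary outcome. Its denominator is inconsistent between Sections IV and VI and open for participants who extend, so the cut-off is 16 or 48 sessions. This should be fixed. It does not show that n=100 is too small.

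**What to change.** 1. **Aim 1.** Make the analysis the overall proportion of participants completing at least 80% of targeted sessions, with an exact two-sided 95% interval. Report disease, age and EDSS groups descriptively.
2. **Sample size.** Replace the power sentence with the precision of n=100, using the intervals for 80/100 and 94/100 above. If a power statement is kept, give its bar, true rate, significance level and test, and confine it to the pooled proportion.
3. **Tolerability.** Drop the power claim. Report the number of participants discontinued under the plan's existing criteria, with an exact two-sided 95% interval.
4. **Denominator.** Reconcile Sections III, IV and VI so that one session target defines the endpoint, including for participants who extend. Which schedule applies is for the investigators to settle.
5. **Wording.** Align the below-80% phrase in Section VIII with the at-least-80% definition in Section III.

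The cost is a few sentences, with no added participants or data. The downside is that the sample-size justification reads less favourably and subgroup results no longer serve as tests of Aim 1.
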